**Table 2-5 Exact 95% CI for different observed event rates at primary analysis**

N	r	95% exact CI using n=600	N	r	Pyrexia event rate (%)	95% exact CI (%)* using n=556
600	92	12.5 - 18.5	556	92	16.5%	13.6 - 19.9
600	93	12.7 - 18.6	556	93	16.7%	13.7 - 20.1
600	100	13.8 - 19.9	556	100	18%	14.9 - 21.4
600	101	13.9 - 20.1	556	101	18.2%	15.0 - 21.6
600	102	14.1 - 20.2	556	102	18.3%	15.2 - 21.8
600	103	14.2 - 20.4	556	103	18.5%	15.4 - 22.0
600	104	14.4 - 20.6	556	104	18.7%	15.5 - 22.2
600	105	14.5 - 20.8	556	105	18.9%	15.7 - 22.4

N: Total numbers of subjects;

r: Number of subjects with pyrexia events at primary analysis

\* Clopper and Pearson (1934)

In addition, the probability that the pyrexia event rate is below the threshold of 20% will be calculated from the posterior distribution. The pyrexia event rate will be assumed to be binary and the number of subjects with pyrexia events will be assumed to follow a binomial distribution. If Y represents the number of patients with composite pyrexia events then predictive distribution of Y conditional on the observed data at the primary is a beta-binomial distribution. A diffuse (highly non-informative) prior distribution of the composite rate with a skeptical expectation of 20%, namely Beta (0.25, 1) will be assumed. For illustration, as shown in [Table 2-6](#), if 96 out of 556 subjects are observed with pyrexia events at primary analysis, then the posterior probability of observing an event rate of < 20% is 0.952 (probability  $\geq$  0.95). This table has been modified for sample size = 556 from the protocol.

**Table 2-6 Posterior probability for a positive effect at primary analysis**

r	Posterior* Pr (event rate<20% data) N= 600	Posterior* Pr (event rate<20% data) N= 556
92	0.999	0.982
96	0.994	0.952
100	0.983	0.890
101	0.977	0.868
102	0.971	0.843
103	0.963	0.816
104	0.954	0.786
105	0.943	0.753
110	0.854	0.559

r	Posterior* Pr (event rate<20% data) N= 600	Posterior* Pr (event rate<20% data) N= 556
115	0.703	0.352
120	0.508	0.183
125	0.313	0.078
130	0.161	0.027
135	0.068	0.007

N: Total numbers of subjects;

r: Number of subjects with pyrexia events at primary analysis

\* A diffuse (highly non-informative) prior distribution of the composite rate with a skeptical expectation of 20%, namely Beta (0.25, 1) is assumed.

### 5.5.3 Handling of missing values/censoring/discontinuations

Only observed events will be summarized in the analysis; incomplete dates of events may be appropriately imputed. For the primary endpoint, patients who discontinued prematurely prior to 12 months without pyrexia will be counted as no event.

### 5.5.4 Supportive analyses

Time to first occurrence of pyrexia will be analysed using the Kaplan-Meier (KM) method. If a patient has not experienced an event by the time of analysis cut-off, the time will be censored at the latest date of study treatment in which the patient is known to be at risk.

The components of the composite primary endpoint (grade  $\geq 3$  pyrexia, hospitalizations due to pyrexia or permanent treatment discontinuation due to pyrexia) will also be analyzed individually by frequency counts in order to evaluate their contributions to the overall treatment effect.

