### **On-treatment assessment/event and observation periods**

For adverse event reporting the overall observation period will be divided into three mutually exclusive segments:

1. **pre-treatment period:** from day of patient's sign informed consent to the day before first administration of study treatment.
2. **on-treatment period:** from date of first administration of study treatment to 30 days after date of last actual administration of any study treatment: dabrafenib or trametinib (including start and stop date).
3. **post-treatment period:** starting at day 31 after last administration of study treatment.

For cases where time of assessment and time of treatment start/stop is captured (e.g. ECG's laboratory assessments), the last available assessment before the treatment period start/stop date/time will be used.

If dates are incomplete in a way that clear assignment to pre-, on-, and post-treatment period cannot be made, then the respective data will be assigned to the on-treatment period. Refer to [section 5.1.1](#) for imputation rules concerning AE start and stop dates.

Safety summaries (tables, figures) include only data from the on-treatment period with the exception of baseline data which will also be summarized where appropriate (e.g. change from baseline summaries). In addition, a separate summary for death including on treatment and post treatment deaths will be provided. In particular, summary tables for adverse events (AEs) will summarize only on-treatment events, with a start date during the on-treatment period (**treatment-emergent** AEs).

However, all safety data (including those from the post-treatment period) will be listed and those collected during the pre-treatment and post-treatment period will be flagged.

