### 5.5.1 Primary endpoint

The primary endpoint is defined as the composite rate of grade 3/4 pyrexia (single preferred term), hospitalizations due to pyrexia or permanent treatment discontinuation due to pyrexia up to 12 months of therapy among overall treated patients.

The rate of this composite primary endpoint is calculated as the total number of patients experiencing at least one of the three components of the composite endpoint (i.e., Grade 3/4 pyrexia, hospitalization due to pyrexia, or permanent treatment discontinuation due to pyrexia), divided by the total number of patients in the FAS. The composite endpoint is assessed over a treatment period of 12 months; that is, any patient who experiences at least one of the components of the composite endpoint anytime within 12 month on-treatment will be included in the numerator for the calculation of the composite rate.

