#### **5.8.5 Additional analyses**

##### **Time to first occurrence**

Time to first occurrence of an event is defined as time from start of study treatment to the date of first occurrence of this event (or first event within an AE grouping), i.e. time in days is calculated as (start date of first occurrence of event) – (start of study treatment) +1.

For Kaplan-Meier analyses of time to occurrence, in the absence of an event during the on-treatment period, the censoring date applied will be **the earliest** of the following dates:

- death date
- new anticancer antineoplastic therapy start date
- end date of on-treatment period
- data cut-off date
- withdrawal of informed consent date.

Failure curves (ascending Kaplan-Meier curves) will be constructed. Median together with 95% confidence interval as well as 25th percentile and 75th percentile will be presented.

In addition, the median time to occurrence for the subset of patients who experienced the event of interest will be calculated. Simple descriptive statistics, median, min and max as well as 25th percentile and 75th percentile, will be presented.

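### SAP 5.5.4 and 5.8.5 give conflicting censoring rules for time to first pyrexia; under 5.5.4 with the general 30-day event window, the curve after about month 11 can be artefactually high

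*SAP*

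**What the plan says.** SAP 5.5.4 (Supportive analyses) plans a Kaplan-Meier analysis of time to first pyrexia. For a subject with no event by the cut-off, "the time will be censored at the latest date of study treatment in which the patient is known to be at risk". It gives no event window and does not refer to another section.

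SAP 5.8.5 (Additional analyses, Time to first occurrence) gives a general rule, with this scope: "For Kaplan-Meier analyses of time to occurrence, in the absence of an event during the on-treatment period". Such a subject is censored at whichever comes first of death, new anticancer therapy, "end date of on-treatment period", data cut-off and withdrawal of consent. It asks for the median with its interval and the 25th and 75th percentiles.

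SAP 5.1.1 defines the on-treatment period as running "from date of first administration of study treatment to 30 days after date of last actual administration of any study treatment". It adds: "Safety summaries (tables, figures) include only data from the on-treatment period" (baseline data excepted).

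SAP 7.1 (Impact of COVID-19) lists six more time-to-first-pyrexia outputs, items 7 to 12, without a censoring rule.

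**The concern.** A Kaplan-Meier estimate needs events and time at risk to be counted over the same period. The 5.8.5 rule does this: both run to 30 days after last dose. The 5.5.4 rule, combined with the general adverse-event window, does not. A subject without fever leaves at last dose, but one whose first fever comes 1 to 30 days later stays at risk until that fever. After last dose, membership of the risk set depends on a future event, and each such event takes a large step out of the curve.

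At stake is the late part of a descriptive figure reported in support of the primary objective, and its 75th percentile. Two programmers following the SAP could also produce different curves from the same data.

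**Working it through.** The documents state no figure for this curve, so there is nothing to reproduce.

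**1. When completers leave the risk set.** Treatment lasts up to 12 study months of 28 days (Protocol 3): 12 × 28 = 336 days. Visits on treatment have a ±3-day window (Protocol Table 8-1, footnote 1), so completers' last doses should cluster near day 336. In SAP reporting months (30.4375 days) that is 336 / 30.4375 = 11.04. The on-treatment period then ends at day 336 + 30 = 366, or 12.02 months.

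**2. One late fever, by hand.** At an event with d cases and n at risk, the event-free estimate S becomes S × (1 − d/n). Take S = 0.37 before the event, from COMBI-AD's 63% any-grade pyrexia (Protocol 1.1). Suppose 200 fever-free subjects finish on day 336 and one of them has a first fever on day 350.

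- 5.5.4 with the 30-day event window: the other 199 are already censored, so n = 1 and S = 0.37 × (1 − 1/1) = 0. The curve jumps to 100%.
- 5.8.5: n = 200 and S = 0.37 × (1 − 1/200) = 0.368. The curve rises by about 0.2 points.

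**3. How many such fevers to expect.** The documents do not say; this is an assumption. As a rough scale, COMBI-AD placebo had pyrexia in 11% over a median 10 months (Protocol 1.1.1.6), about 1.1% per month. With N = 556, that gives 556 × 0.37 × 0.011 = 2.3 first fevers. The range used is 1% and 0.3% per 30 days after last dose.

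**4. Simulation.** N = 556. 63% complete (COMBI-AD, Protocol 1.1.1.6), with last dose at day 336 ± 3; the rest stop uniformly between days 14 and 329. 63% are fever-prone, with exponential onset of mean 60 days (assumed). Either no completers, or 5% of them, dose 1 to 30 days late (assumed).

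| Post-dose first fever per 30 days | Completers dosing late | Day 365 under 5.5.4 | Day 365 under 5.8.5 |
|---|---|---|---|
| 1% | 0% | 88% | 62% |
| 1% | 5% | 75% | 62% |
| 0.3% | 0% | 73% | 62% |
| 0.3% | 5% | 67% | 62% |

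Without late dosing, the 75th percentile is reached under 5.5.4 in about 70% of runs at 1% and about 30% at 0.3%. Under 5.8.5 it is reached in none.

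**5. Fixing the number of post-dose first fevers instead.** Entries are the mean at the end of the curve; the share of runs reaching exactly 100% is in brackets. Late dosing is again 5% of completers, by up to 30 days.

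| Post-dose first fevers | 5.5.4, no late dosing | 5.5.4, late dosing | 5.8.5, no late dosing |
|---|---|---|---|
| 0 | 63% (0%) | 63% (0%) | 62% |
| 1 | 85% (60%) | 71% (11%) | 62% |
| 2 | 92% (78%) | 76% (15%) | 62% |
| 4 | 99% (97%) | 84% (30%) | 63% |

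Crude incidence in these runs is 59% to 60%.

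**6. What hardly moves.** At day 330 the curves stand at about 63% and 62%. The median differs by 3 to 4 days.

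**The case against.** The best defence is that 5.5.4 does not contain the mismatch. It states no event window; the 30 days come from 5.1.1. Protocol 6.5.1.1 defines pyrexia for this study as fever during study treatment. Counting only fevers up to last dose, and censoring there, is coherent and removes the artefact. The words in 5.5.4 about being known to be at risk could also be stretched to the end of the on-treatment period, which would agree with 5.8.5.

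Either reading would work, but the SAP adopts neither. Section 5.5.4 ties its censoring date to study treatment. Its test for having no event refers to the analysis cut-off, not to last dose. The general rule for safety tables and figures includes the 30-day tail. The primary endpoint text counts events "anytime within 12 month on-treatment will be included in the numerator", which also does not settle whether the tail belongs.

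A second defence is that 5.8.5 already holds a sound rule. That is true, and it makes the repair easy. But 5.8.5 is the general section and 5.5.4 the one specific to pyrexia, so a programmer could reasonably follow 5.5.4.

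The size is also fragile. It depends on an unknown number of post-dose fevers and on how tightly last doses cluster. With 5% of completers dosing late, the day-365 excess over 62% falls from 26 points to 13 at the 1% rate, and from 11 to 5 at 0.3%. This objection stands, and is why a range is given.

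**Conclusion.** The conflict between 5.5.4 and 5.8.5 is on the page and needs no assumption. That 5.5.4 produces an artefact is conditional: the 30-day event window must apply, and at least one first fever must fall after last dose when few subjects are still dosing. On those terms the day-365 estimate is about 67% to 88% instead of 62%, for 0.3% to 1% post-dose first fevers and 0% to 5% of completers dosing late. The 75th percentile may be reached when it should not be.

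A reader might infer more than the documents support:

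- That 5.5.4 itself counts fevers to 30 days after last dose. It is silent on this.
- That the curve must end at 100%. It can, but it does not climb if no first fever follows last dose.
- That percentiles in general are biased. The first quartile and median fall well before month 11 and barely change, and the SAP sets no landmark estimate for this curve.
- That this is the only time-to-event analysis of pyrexia. SAP 7.1 lists others, subject to minimum numbers.
- That the primary conclusion is at risk. The curve is descriptive and concerns any pyrexia, not the composite. The primary test is an exact interval on a proportion of the full analysis set (SAP 5.5.2), with no Kaplan-Meier censoring.

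The change should be made because it removes a possible bias from a reported curve at almost no cost.

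**What to change.** In SAP 5.5.4, replace the censoring sentence with a reference to the 5.8.5 rule. If last-dose censoring is preferred, keep it and state that only fevers starting on or before last dose count as events. Either way, state the event window in 5.5.4 and apply the same rule to every time-to-first-pyrexia output, including items 7 to 12 of SAP 7.1.

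The cost is one sentence in the SAP and one line of derivation code. There is a small downside: the SAP addendum describes the final analysis as a re-run of the primary analyses. If the primary-analysis outputs used the other rule, the two reports will differ and the final output needs a footnote saying so.

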## 5.6 Analysis of the key secondary objective

Not applicable.

## 5.7 Analysis of the secondary objective(s)

The secondary efficacy objectives are to

- Evaluate the relapse free survival (RFS) at 12 and 24 months.
- Evaluate overall survival (OS) rate at 12 and 24 months.
- Evaluate patients' quality of life with respect to patient reported outcomes (PROs) of functional assessment of cancer therapy–melanoma (FACT-M) melanoma subscales.

## 5.7.1 Secondary endpoints

### Relapse free survival

RFS is defined as the time from the date of first dose of the study treatment to the date of the first documented disease recurrence or death due to any cause whichever comes first. Treatment emergent malignancies other than second melanomas will not be considered as events. The analysis will be based on FAS and will include all data observed up-to the cut-off date.

RFS will be censored if no RFS event is observed before the first to occur between: (i) the analysis cut-off date, and (ii) the date when a new anti-cancer therapy is started. The censoring date will be the date of the last adequate tumor assessment prior to data cut-off date/start of new anti-cancer therapy date (see [Section 2.7.3](#) for additional details regarding censoring rules and determination of date of last adequate tumor assessment).

### Overall survival

OS is defined as the time from start date of study treatment to date of death due to any cause. All deaths occurring on or before the cut-off date in the FAS will be used in the OS analysis.

If a patient is not known to have died, then OS will be censored at the last contact date when the patient was known to be alive (on or before the cut-off date) (see [Section 2.1.1](#) for the derivation of the last contact date).

### Functional assessment of cancer therapy-melanoma (FACT-M)

FACT-M will be used to evaluate patient-reported outcome measures of health-related quality-of-life, functioning, disease symptoms, treatment-related side effects, and global health status. The Melanoma Subscale of the FACT-M are recognized as reliable and valid measures ([Cormier 2008](#)) frequently used in clinical trials of patients with advanced or metastatic cancer.

The FACT-M quality of life questionnaire consists of the FACT-General (FACT-G) plus the Melanoma Subscale and the Melanoma Surgery Subscale, which complement the general scale with items specific to health-related quality of life (HRQOL) in melanoma. For the purpose of this study the 16 items that comprise the Melanoma Subscale (MS) of the FACT-M are used.

## 5.7.2 Statistical hypothesis, model and method of analysis

RFS and OS will be analyzed descriptively in the FAS population. The RFS and OS distribution will be estimated using the Kaplan-Meier method. The Kaplan-Meier estimates will be plotted graphically. The median, 25th and 75th percentiles of RFS and OS along with 95% confidence intervals [Brookmeyer and Crowley 1982] will be presented.

The survival probabilities at 12 and 24 months, and the associated 95% confidence intervals will be summarized. The percentage of surviving subjects who are alive and disease free 1 year intervals from the time of first treatment will be estimated from the Kaplan-Meier curves for the RFS. The probabilities will be calculated at 1 year and at 2 years. Approximate 95%

confidence intervals will be calculated, based on Greenwood's formula for the standard error (SE) of the Kaplan-Meier estimate. The similar analysis will be presented for the OS as well.

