Approximately 600 subjects will be enrolled to receive dabrafenib (150 mg BID) and trametinib (2 mg once daily) combination therapy for 12 months. At Day 1, subjects will be instructed on the pyrexia management algorithm (refer to [Section 6.5.1.1](#)). Doses of study treatment may be modified and/or interrupted for management of toxicities associated with study treatment ([Section 6.5.1.1](#)). There will be an IA of the primary endpoint and secondary efficacy endpoint RFS when approximately the first 200 subjects dosed have been followed for 6 months (either completed 6 months of treatment or discontinued treatment earlier (see [Section 4.4](#)).

For this study, one study month is equal to 4 weeks or 28 days.

This study consists of two Periods for Enrolled subjects:

- Treatment Period – subjects will receive up to 12 months of treatment (refer to the schedule as noted in [Table 8-1](#)).
- Follow-up Period – subjects will be followed from treatment discontinuation through 24 months from their first dose date for relapse; and will be followed for overall survival through withdrawal, lost to follow-up, death, or the end of study (see definition in [Section 9.2](#)), whichever occurs first. Follow-up will start once: 1) treatment is completed; or 2) is prematurely discontinued and continue until withdrawal, lost to follow-up, death, or the end of study even if disease recurs. Follow-up contact prior to disease recurrence and through the 24 month assessment will include clinic visits (refer to the schedule as noted in [Table 8-2](#)). Follow-up after disease recurrence and until EoS should follow the schedule as noted in [Table 8-3](#).

Figure 3-1 Study design

4 Rationale

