The rate of the composite primary endpoint is defined as the total number of subjects experiencing at least one of the three components of the composite endpoint (i.e., Grade 3/4 pyrexia, hospitalization due to pyrexia, or permanent treatment discontinuation due to pyrexia), divided by the total number of subjects treated in the study. In the COMBI-AD study, 23 (5%)

subjects had grade 3/4 pyrexia, 46 (11%) subjects were hospitalized due to pyrexia and 38 (9%) subjects permanently discontinued due to pyrexia. In total, in COMBI-AD, 87 out of 435 subjects in the treatment arm (20%) developed either grade 3/4 pyrexia or hospitalization due to pyrexia or discontinued due to pyrexia. This rate of 20% will be used as the historical control rate for the assessment of pyrexia management algorithm in this study.

In the absence of control arm in the study, the composite rate due to adverse outcomes of pyrexia in the study will be compared with the 20% historical rate observed in COMBI-AD study.

As this is the first trial to prospectively test the algorithm, an IA of the primary endpoint and secondary efficacy endpoint RFS at 6 months is planned which will allow assessing the futility of the adapted algorithm. Please refer to [Section 4.4](#).

The secondary endpoints of RFS and OS (12 and 24 months) will be assessed across both periods in the study based on efficacy assessment guidelines in the COMBI-AD study. Subjects will be followed up to EoS, death, withdrawal of consent, or lost to follow-up, whichever occurs first, but will only have on-study tumor assessments through 24 months after first dose of study treatment. Other secondary endpoints include the evaluation of the overall adverse events rate leading to permanent treatment discontinuation at 12 months, overall safety and tolerability, as well as patient-reported outcomes (FACT-M) through 24 months.

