If early treatment discontinuation occurs due to reason other than disease relapse or a subject has completed treatment and has not relapsed, refer to [Table 8-2](#).

Table 8-2 Follow-up (Pre-Relapse) Assessment Schedule

	Pre-Relapse Visit & Assessment Schedule ¹							
Visit Name	Month 3	Month 6	Month 12	Month 15	Month 18	Month 24	Survival Contact (every 3 mo) ²	End of Study (EoS) ³
Physical Examination	X	X	X	X	X	X		X ³
ECOG Performance Status	X	X	X	X	X	X		X ³
Chest, abdomen and pelvic CT scans ⁴	X	X	X	X	X	X		X ³
Dermatologic Assessment	X	X	X	X	X	X		X ³
Patient reported outcomes	X	X	X	X	X	X		X ³
Any anti-neoplastic therapy (including surgery, radiotherapy, medications) since discontinuation of study treatment including Best Response	X	X	X	X	X	X	X	X
Survival Follow Up	X	X	X	X	X	X	X	X
Disposition Assessment (at the end of each study period)								X

¹ Follow-up will start once treatment is completed or discontinued and should continue through EoS Visit, withdrawal or death, even if disease recurs. Follow-up visits prior to disease recurrence should follow [Table 8-2](#), and should be clinic visits through the Month 24 Assessment. Follow-up visits after the Month 24 Assessment are not required to be clinic visits and the information collected will be limited to the following: any radiotherapy; surgical procedure or new anti-cancer therapy initiated until EoS visit, withdrawal or death; best response to any follow-up treatment; and survival data. For example, if a subject discontinues treatment at Month 2 for reason other than disease relapse, the EoS should be performed according to [Table 8-1](#) and the follow-up assessments would start at Month 3 according to [Table 8-2](#) until EoS, withdrawal or death. Follow-up after disease relapse should follow the schedule in [Table 8-3](#).

² Survival follow-up after the Month 24 assessment should be conducted every 3 months until withdrawal, death, or study end (whichever occurs first), and can be done via phone contact.

³The EoS visit should be completed at withdrawal, lost to follow-up, death, or at the end of study (see definition in [Section 9.2](#)), whichever occurs first. If the EoS visit occurs after the Month 24 visit, a clinic visit is not required and the information collected will be limited to the following: anti-cancer therapy, best response to any follow-up treatment, and survival data

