8.3.1.1 Assessment Guideline

Assessments must be performed on a calendar schedule and should not be affected by dose interruptions/delays. For post-baseline efficacy assessments Month 1 through Month 12, a window of ± 3 days (physical exam) or ± 7 days (CT scans, dermatologic skin assessment) is permitted to allow for flexible scheduling. After Month 12/EoT a post-baseline assessment window of ± 14 days is permitted.

The following are required for efficacy assessment:

- Clinical examination
- Diagnostic quality, contrast-enhanced CT scan of the chest, abdomen and pelvis should be performed at baseline and subsequent timepoints as indicated in [Table 8-1](#), [Table 8-2](#), and [Table 8-4](#). Intravenous contrast should be used for the CT scans preferably with oral contrast as well. CT contrast of the chest, with contrast-enhanced MRI of the abdomen and pelvis should be substituted for full CT scanning if the CT frequency prescribed in [Table 8-1](#), [Table 8-2](#), and [Table 8-4](#) is not permitted per country or ethics requirements or if CT contrast is contraindicated. The method of imaging, including use of contrast, should be consistent throughout the study (i.e. if CT is done at screening, CT will be done at all future timepoints), where not contraindicated.
- A baseline MRI of the brain is required for all subjects. CT may be performed. Subsequent brain scans should only be performed as clinically indicated (e.g. symptoms suggestive of CNS recurrence). Contrast enhanced brain MRI is preferred, however, if MRI contrast is contraindicated, then MRI without contrast or CT with/without contrast is acceptable.
- Biopsy of suspected recurrences is strongly recommended to confirm the diagnosis.
- Ultrasound is not a suitable modality of disease assessment for distant metastases. If new lesions are identified by ultrasound, confirmation by CT or MRI is required.
- If clinically indicated, CT or MRI of other areas (e.g., neck) of disease as appropriate should be performed.
- Fluorodeoxyglucose positron emission tomography (FDG)-PET can be useful in confirming new sites of disease where a positive FDG-PET scans correlates with the new site of disease present on CT/MRI or when a baseline FDG-PET was previously negative for the site of the new lesion.
- If PET/CT is performed then the CT component can only be used for standard disease assessments if performed to diagnostic quality, which includes the required anatomical

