- Follow-up Period – subjects will be followed from treatment discontinuation through 24 months from their first dose date for relapse; and will be followed for overall survival through withdrawal, lost to follow-up, death, or the end of study (see definition in protocol Section 9.2), whichever occurs first. Follow-up will start once: 1) treatment is completed; or 2) is prematurely discontinued and continue until withdrawal, lost to follow-up, death, or the end of study even if disease recurs. Follow-up contact prior to disease recurrence and through the 24 month assessment will include clinic visits (refer to the schedule as noted in protocol Table 8-2). Follow-up after disease recurrence and until EoS should follow the schedule as noted in protocol Table 8-3.

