### **Time units**

A year length is defined as 365.25 days. A month length is 30.4375 days (365.25/12). If duration is reported in months, duration in days will be divided by 30.4375. If duration is reported in years, duration in days will be divided by 365.25.

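### 24-month RFS is read at day 730.5, but the last numbered relapse assessment is day 673, and the protocol conflicts on whether a later end-of-study scan keeps anyone at risk

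*SAP*

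**What the plan says.** **Reading time.** SAP 5.7.2 takes RFS from the Kaplan-Meier curve: "The probabilities will be calculated at 1 year and at 2 years". Under Time units in SAP 5.1.1, a year is 365.25 days and "A month length is 30.4375 days (365.25/12").

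**Visit time.** Protocol section 3 uses another month: "For this study, one study month is equal to 4 weeks or 28 days". Protocol 8.3.1.3 counts imaging from Day 1. Table 8-4 lists scans at Months 3, 6, 12, 15, 18 and 24. On timing, Protocol 8.3.1.1 says: "After Month 12/EoT a post-baseline assessment window of" 14 days either way.

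**Censoring.** SAP 5.7.3 and its Table 2-7 on RFS outcomes censor a subject without relapse or death at the last efficacy assessment.

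**Assessments after Month 24.** The protocol points two ways.
- Towards a later scan: the EoS row of Table 8-4 asks for one if the previous scan is more than 30 days old and there has been no recurrence or other anti-cancer therapy. Protocol 8.3.1.3 lets imaging run to a combined 24-month/EoS assessment.
- Away from one: under Protocol 4.1 subjects are followed to EoS, "but will only have on-study tumor assessments through 24 months after first dose of study treatment". Table 8-2 note 1 says "Follow-up visits after the Month 24 Assessment are not required to be clinic visits and the information collected will be limited to the following" and then lists therapy, best response and survival. Note 3 says "If the EoS visit occurs after the Month 24 visit, a clinic visit is not required" and restricts the data in the same way.
- Both ways: the text of Protocol 8.3.1 continues tumor assessments until EoS, yet glosses this as meaning up to Month 24.

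The SAP does not settle it. Its section 4 says only that "subjects will be followed from treatment discontinuation through 24 months from their first dose date for relapse".

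**The concern.** The analysis clock and the visit clock differ by almost two months at this landmark, and the censoring rule turns that gap into an estimation problem. A subject who is relapse-free at Month 24 and has no later assessment leaves the risk set at that visit, before the day on which the curve is read. Whether anyone is still at risk at two years then depends on a scan that one part of the protocol requests and another part leaves out.

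RFS at 24 months is a named secondary endpoint, reported with a 95% interval. It is descriptive and carries no test. What is at stake is whether the reported figure rests on subjects actually under observation at two years.

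**Working it through.** **1. Reproduce the plan's own time scales.** 365.25 / 12 = 30.4375, as the SAP states. The SAP visit-window formula d = 28k + 1 gives day 85 for Month 3 and day 113 for Month 4, as in its table.

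**2. Reading day.** 2 × 365.25 = 24 × 30.4375 = 730.5.

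**3. Last numbered assessment.** 24 × 28 + 1 = day 673, which is 673 / 30.4375 = 22.1 calendar months. The window is 673 ± 14, or day 659 to day 687. The shortfall is 730.5 − 673 = 57.5 days nominally and 730.5 − 687 = 43.5 days at the late edge.

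**4. Risk set without an EoS scan.** Every event-free subject scanned in window is censored by day 687, so none is at risk at day 730.5. Physical examinations also count as efficacy assessments, but Table 8-2 notes 1 and 3 drop them after Month 24. Those who can remain are subjects with a late scan or with a later recorded event, such as a death.

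**5. Risk set with an EoS scan.** Protocol 9.2 places EoS 24 months after the last subject's Day 1. A subject first dosed g days earlier has EoS at about day 673 + g (28-day months) or 731 + g (calendar months). Reaching day 730.5 needs g ≥ 57.5 in the first case; essentially everyone qualifies in the second.

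**6. Size, by simulation.** From the documents: N = 556 (SAP), and 12-month RFS of 88% (95% CI 85% to 91%) in the historical treatment arm (Protocol 12.7). Assumed: constant hazard, so the true values are 0.88² = 0.774 at day 730.5 and 0.88^(673/365.25) = 0.790 at day 673; scans uniform within their windows; 20% of relapses found between scans.

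| No EoS scan | Mean estimate at day 730.5 (true 0.774) |
|---|---|
| Base case, whole-day dates, 0 at risk | 0.67 to 0.68 |
| Unrounded dates | about 0.60 |
| Scan scatter ±7, ±3, 0 days | 0.70, 0.72, 0.79 |
| 0% or 50% of relapses found between scans | 0.64, 0.71 |
| 20% or 40% of Month 24 scans up to 60 days after day 687 (25 or 51 at risk) | 0.71, 0.73 |
| SAP 8.1.1.1 dating, investigations close to the visit date | about 0.72 to 0.77 |
| SAP 8.1.1.1 dating, 2 or 3 investigations spread over the window | 0.78, 0.79 |

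The SAP 8.1.1.1 rule dates a non-progressing assessment by its latest investigation and a progressing one by its earliest. If the 12-month rate is 85% or 91%, the base case gives 0.60 against 0.722, or 0.74 against 0.828. A harsher variant still records relapses found clinically after Month 24 and gave 0.55 to 0.58. It is left out of the quoted range because the Table 8-2 notes would not collect them.

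| EoS scan | Estimate at day 730.5 | At risk |
|---|---|---|
| Done | 0.785 to 0.788 | 364 to 438 |
| Half done | 0.769 to 0.773 | 181 to 220 |

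These cases use the accrual counts in the protocol's amendment history (37 treated by 30-Nov-2018, 234 by 12-Mar-2019). They assume a first dose on 1-Aug-2018 and a last first dose on 26-Sep or 26-Oct-2019.

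**7. Alternative reading at day 673.** Base case 0.803 against 0.790, about 239 at risk. It is up to 0.814 if 40% of Month 24 scans are late, and 0.809 to 0.810 if EoS scans are done. It therefore reads about 1 to 2.5 points high.

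**8. 12-month reading.** Day 365.25 lies between Month 12 (day 337) and Month 15 (day 421). Base case at the final analysis: 0.887 against 0.880, 493 at risk.

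**The case against.** **EoS scans may well be done.** Table 8-4 asks for them. In that case hundreds remain at risk and day 730.5 is a sound reading. This stands, and it is why the conclusion is conditional.

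**The error has no fixed size or direction.** The bias arises because relapses and censorings interleave inside the Month 24 window. The earliest/latest dating rule pulls relapses earlier and pushes censorings later, which undoes much of it. With no scan scatter the estimate is slightly high. This largely stands. The rule sits under a heading on incomplete dates, so its reach is unclear, and the number and spread of investigations per visit are assumed.

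**A misleading value may never be printed.** SAP 8.4.2 names the procedure but does not say what is shown beyond the last follow-up time, and the table shells, which may already carry numbers at risk, are in a separate document. This stands: neither a carried-forward value nor a missing at-risk row can be asserted.

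**Day 673 has faults of its own.** It falls mid-window, reads high, and puts the 12- and 24-month landmarks on different month scales. If EoS scans were done, it is the worse choice. This stands and limits the fix.

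**It is late to change scans.** The latest SAP entry is dated 20 July 2021, shortly before final lock. So the SAP statement on which assessments count matters more than a protocol change.

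None of this removes the gap between the two clocks or the conflict over the EoS scan.

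**Conclusion.** The point holds in conditional form. The mismatch (day 730.5 against day 673, window end 687) and the conflict over the EoS scan are in the text and need no simulation. If no EoS scan is done and visits fall in window, essentially no event-free subject is at risk at the 24-month reading. The value is then either not estimable or carried forward from a risk set that emptied inside the Month 24 window. Under the assumptions above, a carried-forward value runs from about 0.60 to 0.79 against a true 0.774, and is about 0.72 to 0.77 in most cases under the SAP 8.1.1.1 dating rule. If EoS scans are done, about 360 to 440 are at risk and the error is about 1 point.

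Two stronger readings are tempting.
- A reader might infer that 24-month RFS will come out about 10 points low, with an interval that usually misses the truth (46% coverage in the base case). The documents do not support this: it is one dating assumption among several, and others bring the error close to zero or slightly high.
- A reader might infer that the risk set will certainly be empty. Table 8-4 asks for the very scan that would fill it.

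The primary endpoint, OS and 12-month RFS at the final analysis are essentially unaffected. The matter should be settled before the final analysis, but it concerns a descriptive secondary endpoint.

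**What to change.** 1. Reconcile Table 8-4 (EoS row), Protocol 8.3.1 and 8.3.1.3 with Table 8-2 notes 1 and 3 and Protocol 4.1.
2. State in the SAP which relapse assessments after Month 24 enter RFS.
3. Print the number at risk at each RFS landmark.
4. Keep day 730.5 if EoS scans leave an adequate number at risk, with that number fixed in advance. Otherwise report the 2-year value as not estimable and give RFS at study Month 24 (day 673), with the existing event and censoring dates, labelled as 28-day months (about 22.1 calendar months).

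The cost is one clarification, one or two SAP sentences and an at-risk row. If day 673 is used, the landmark is shorter than two years, is on a different month scale from the 12-month reading, and is about 1 to 2.5 points high.
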